**Table 1.**

	Screening Randomization	1 day after DSO	7 ± 2 days after DSO	3 ± 1 weeks after DSO	5 ± 1 weeks after DSO	7 ± 1 weeks after DSO	9 ± 1 weeks after DSO	Exit visit 12 ± 2 wks after DSO
Informed Consent	X							
Inclusion/Exclusion Criteria	X							
Medical and ophthalmic history	X	X	X	X	X	X	X	X
Adverse Events	X	X	X	X	X	X	X	X
Uncorrected visual acuity (Snellen)	X	X	X	X	X	X	X	X
Visual disability questionnaire	X			X	X	X	X	X
Assignment to netarsudil or placebo	X							
Manifest refraction and corrected distance vision (Snellen) if possible	X			X	X	X	X	X
Slit lamp exam	X	X	X	X	X	X	X	X
Endothelial cell density (if possible)							X	X
Intraocular pressure	X				X	X	X	X
Ultrasonic pachymetry	X				X	X	X	X
Anterior segment optical coherence tomography	X			X	X	X	X	X

### 3.2 Data Analysis and Data Monitoring:

The primary endpoint is the proportion of corneal clearing at 4 and 6 weeks after DSO. Based on previous pilot studies, we estimate that the mean proportion of corneal clearing in the placebo

arm will be 0.6 vs. 0.8 in the Rhopressa arm. The standard deviation is estimated to be  $\pm 0.30$ . A sample size of 29 per study arm (total = 58) would provide 80% power to detect a statistically significant difference between groups at a 5% significance level (one-sided test). The planned enrollment is 60 subjects; this anticipates 3% drop out prior to the 4-week primary endpoint.

Statistical analysis will be conducted on an intent-to-treat basis (i.e. all randomized subjects will be included in the analysis). Data will be analyzed with Statistical Analysis Software (SAS Version 9.4, SAS Institute, Cary, NC).

**3.3 Data Storage and Confidentiality:** Research data will be stored in a locked cabinet or locked room and on a password protected server to prevent unauthorized access to data. The investigators and research staff will have access to the data. Subject identifiers will be removed and data will be aggregated for publication or presentation of study results.

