### **1.3 Study Design**

- Prospective, randomized, double-masked, placebo-controlled clinical trial
- Main Outcome Measure: rate of corneal clearing after DSO for FECD

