## **3.0 Methods & Procedures**

### **3.1 Study procedures and assessments.**

- Screening and Enrollment: Prospective subjects will be considered for entry into the study. Subjects meeting the inclusion and exclusion criteria will be informed of the opportunity to participate in the study. Subjects will be entered into the study after providing written informed consent. Each subject will be instructed that if they decide not to participate, they may withdraw at any time.
- Randomization: Netarsudil ophthalmic solution 0.02% and placebo eye drops will be dispensed to study subjects in 2.5 ml bottles, identical in appearance. A designated, unmasked, dosing coordinator will apply a coded sticker to each bottle. A computer generated randomization table will be generated. After the study subject signs the informed consent document, the subject will be randomly assigned to receive netarsudil or placebo (netarsudil vehicle). Both the subject and the investigator will remain masked as to the assigned treatment. If a study participant elects to have both eyes enrolled in the study, the dosing coordinator will automatically assign the second eye to the opposite treatment group from that of the first eye.
- Study Treatment Regimen: Subjects will be instructed to instill the assigned eye drop into the study eye once nightly for the 3-month study duration or until 2 weeks after corneal clearing is complete, whichever occurs sooner.

- Study Drug Accountability: Subjects will be asked to bring back to the clinic all study bottles, both used and un-used. All study drug bottles will be reconciled and recorded.
- Rescue Medication: If corneal clearing is not complete or seems to have stalled at the 5-week exam, the investigator can ask the dosing study coordinator to reveal the randomization assignment. If the eye was randomized to placebo it can be treated once daily (at night) with netarsudil (open label) for 7 weeks, whereas if the eye was originally randomized to netarsudil, it can be treated twice daily with netarsudil (open label) for 7 weeks or until complete clearing, whichever is sooner, in lieu of using the masked study drop.
- Examinations:
  - Schedule: Study visits include screening, as well as 1 day, 1 week, 3 weeks, 5 weeks, 7 weeks, 9 weeks and 12 weeks after DSO (Table 1). If complete healing is noted at the 3-, 5- or 7-week exam, the next following exam can be omitted.

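### The primary endpoint is set at 4 and 6 weeks, but exams are scheduled at 3, 5 and 7 weeks and no rule says which exam supplies which value

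*Combined protocol and SAP*

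**What the plan says.** Section 3.2 of the combined protocol and SAP defines the endpoint: "The primary endpoint is the proportion of corneal clearing at 4 and 6 weeks after DSO". The sample size paragraph in the same section plans on mean clearing of 0.6 versus 0.8 with SD 0.30, and says of the planned enrolment that "this anticipates 3% drop out prior to the 4-week primary endpoint". The analysis is intent-to-treat, so that "all randomized subjects will be included in the analysis". Section 1.3 gives the main outcome as "rate of corneal clearing after DSO for FECD", with no time attached.

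Section 3.1 (Examinations) lists the visits after screening as "1 day, 1 week, 3 weeks, 5 weeks, 7 weeks, 9 weeks and 12 weeks after DSO". Table 1 adds windows of ±1 week to the 3-, 5-, 7- and 9-week visits. Clearing is graded by slit lamp at each visit. The schedule also allows a skip: "If complete healing is noted at the 3-, 5- or 7-week exam, the next following exam can be omitted".

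The rescue paragraph of section 3.1 applies "If corneal clearing is not complete or seems to have stalled at the 5-week exam". In that case "the investigator can ask the dosing study coordinator to reveal the randomization assignment", and the eye may move to open-label netarsudil whichever arm it was in.

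**The concern.** The two endpoint times do not exist in the visit schedule, and section 3.2 is not consistent on whether there are two times or one. No text assigns an exam to week 4 or week 6, defines interpolation, or says what to do when two exams qualify. Two analysts could each follow the plan faithfully and report different primary results.

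The ambiguity has consequences because the 5-week exam is the point at which the code may be broken and treatment changed. A 6-week value taken from the 5-week exam compares the arms under masked treatment. A 6-week value taken from the 7-week exam may include placebo eyes already on netarsudil and netarsudil eyes on a changed regimen. These are different questions. If the choice is left open, it could be made after assignments are known.

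**Working it through.** **1. The plan's own figure.** Inputs from section 3.2: difference 0.8 − 0.6 = 0.20, SD 0.30, 29 per arm, one-sided 5%. For a two-sample t-test:

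- standard error = 0.30 × √(2/29) = 0.0788
- noncentrality = 0.20 / 0.0788 = 2.54, with 56 degrees of freedom
- power = 80.6%, and 29 is the smallest number per arm that reaches 80%
- dropout: 58 / (1 − 0.03) = 59.8, rounded up to 60

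The stated sample size reproduces. What section 3.2 does not say is which scheduled exam the 0.6, 0.8 and 0.30 describe.

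**2. Endpoint times against visit windows (section 3.1 and Table 1).**

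| Visit | Window (weeks) | Distance from week 4 | Distance from week 6 |
|---|---|---|---|
| 3±1 | 2 to 4 | 1 | 3 |
| 5±1 | 4 to 6 | 1 | 1 |
| 7±1 | 6 to 8 | 3 | 1 |

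Week 4 is the last point of one window and the first of the next, and so is week 6. A nearest-visit rule based on nominal times would tie at both. The 4-week value could come from an exam held anywhere from week 2 to week 6, and the 6-week value from week 4 to week 8. A single 5-week exam could serve as both.

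**3. Position relative to rescue.**

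- *4-week value:* the candidates are the 3- and 5-week exams. Both come before that eye's own rescue decision, so rescue does not affect it.
- *6-week value from the 5-week exam:* before that eye's rescue decision.
- *6-week value from the 7-week exam:* possibly after it. If open-label treatment starts on the day of the 5-week exam (an assumption; the plan gives no start day), the time on it is the gap between the two exams. For any in-window pair this runs from 6 − 6 = 0 to 8 − 4 = 4 weeks, and is 7 − 5 = 2 weeks at nominal times. For a 7-week exam held exactly at week 6 it runs from 6 − 6 = 0 to 6 − 4 = 2 weeks. The zero arises only if both exams fall at week 6.

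Rescue is optional, limited to incomplete or stalled eyes, and open to both arms. The documents give no rescue rate, so the share of eyes affected and the net shift cannot be calculated.

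**4. Omitted exams.** An eye healed at week 3 may skip week 5, but it has the 3-week exam next to week 4 and is still due at week 7, next to week 6. An eye healed at week 5 may skip week 7, but its 5-week exam adjoins both endpoint times. A permitted omission therefore never leaves week 4 or week 6 without an adjacent scheduled exam.

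**The case against.** The strongest reply is that 4 and 6 weeks are the limits of the 5±1 window, so the sponsor simply meant the 5-week visit. That is possible. But it is not written, and it does not fit the dropout sentence, which names a single 4-week endpoint. If it was the intention, one sentence settles the matter.

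A second reply is that clearing is graded at every visit, so data around both times will normally exist. This stands. The gap is in the selection rule, not in the data collection, and it can be closed by wording. The undated outcome in section 1.3 is a one-line design summary and is not a contradiction in itself.

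A reader might infer three stronger things that the documents do not support:

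- *Healed eyes that skip an exam would be lost, distorting the 0.20 difference.* Step 4 shows that an adjacent exam always remains, and leaving such eyes out would contradict the rule that all randomized subjects are analysed. Any figure for the distortion would also need skipping rates that the plan does not give.
- *The result is biased in a known direction.* Rescue is open to both arms and its frequency is unknown, so no direction follows.
- *Second eyes should be set aside where a first-eye code break reveals their assignment, since they receive the opposite arm.* That is a separate masking question. Such an exclusion after randomization would itself depend on treatment arm, so it is not proposed here.

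**Conclusion.** The point holds in this form: the endpoint times in section 3.2 do not match the visit schedule in section 3.1 and Table 1, section 3.2 is inconsistent about one time or two, and the primary endpoint cannot be computed uniquely as written. The practical consequence is confined to the 6-week value, which may precede rescue or follow up to 4 weeks of open-label netarsudil depending on the exam chosen. That upper limit assumes in-window exams and rescue started at the 5-week exam. The effect on the treatment difference cannot be sized or signed from the documents. The sample size calculation is not challenged. This should be fixed; because exams adjoin both times, wording settled before unmasking is enough.

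**What to change.** Before any unmasked analysis, reconcile sections 3.1 and 3.2 and Table 1 by tying the primary endpoint to scheduled visits. Either of two routes would do.

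**One visit.** For example:

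> The primary endpoint is the proportion of corneal clearing at the 5-week visit (5±1 weeks, identified by visit label), graded before that eye's own rescue decision or code break. An eye completely healed at the 3-week exam whose 5-week exam was omitted is analysed as 1.0.

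The last sentence is needed because this wording names an exam that may be skipped. It agrees with including all randomized subjects. A 5-week exam missed for any other reason needs its own stated rule.

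**Two times.** Keep both, name one visit for each, and state how values after rescue are handled and how the two times share the one-sided 5%. If the 5% were split equally (an assumption), the calculation in step 1 gives 70.4% power at each time with 29 per arm. A fixed testing order would keep 80.6% for the time tested first.

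Under either route, state which visit the 0.6, 0.8 and SD 0.30 and the 3% dropout refer to.

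The cost is protocol and SAP wording plus one check of the pilot data, with no new visit or procedure. The downside is that the nominal endpoint time may shift by about a week; if the planning values do not hold at the named visit, the sample size must be recalculated. No change to the clinical rescue rule is proposed.

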### **2.0 Characteristics of the Research Population**

2.1 **Number of Subjects:** up to 60 FECD patients will be enrolled.

2.2 **Gender of Subjects:** both men and women will be enrolled

2.3 **Age of Subjects:** 18-90 years of age. The rationale for not including minors is that endothelial keratoplasty is performed to treat endothelial dysfunction, a condition usually seen in adults over 40 years of age.

2.4 **Racial and Ethnic Origin:** Subjects may be of any racial or ethnic origin.

2.5 **Inclusion criteria.** The following are requirements for study inclusion:

- At least 18 years of age
- Male or female patient undergoing Descemet stripping only for Fuchs dystrophy.
- Patient is able and willing to administer eye drops.
- Patient is able to comprehend and has signed the Informed Consent form.

**2.6: Exclusion criteria.** Patients with any of the following cannot participate in the study:

- Active intraocular inflammation, corneal ulceration, keratitis, or conjunctivitis.
- Known sensitivity to any of the ingredients in the study medications.
- Abnormal eyelid function.
- History of herpetic keratitis.
- History of non-compliance with using prescribed medication.
- Current or planned pregnancy within the study duration.
- Concurrent involvement or participation in another randomized clinical trial within 30 days prior to enrollment in this study.
- Any ocular or systemic condition (i.e., UNCONTROLLED systemic disease) or situation which in the investigator's opinion may put the patient at significant

risk, confound the study results, or interfere significantly with the patient's participation in the study.

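### The primary endpoint names two time points, weeks 4 and 6, with no rule linking them, so the stated 5% error and 80% power are not both assured.

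*Combined protocol and SAP*

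**What the plan says.** Section 3.2 defines the endpoint: "The primary endpoint is the proportion of corneal clearing at 4 and 6 weeks after DSO". It then assumes one pair of mean clearing proportions (0.6 on placebo, 0.8 on Rhopressa) and one SD (0.30), tied to neither week. At a one-sided 5% level it concludes: "A sample size of 29 per study arm (total = 58) would provide 80% power to detect a statistically significant difference between groups". Planned enrolment is 60, and of that number it says: "this anticipates 3% drop out prior to the 4-week primary endpoint". The rest of the analysis text specifies only intent-to-treat and the software. It names no primary test, order of testing, multiplicity rule or success rule.

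Section 3.1 schedules exams at "1 day, 1 week, 3 weeks, 5 weeks, 7 weeks, 9 weeks and 12 weeks after DSO", so none falls nominally at week 4 or week 6. It adds: "If complete healing is noted at the 3-, 5- or 7-week exam, the next following exam can be omitted". On rescue it says: "If corneal clearing is not complete or seems to have stalled at the 5-week exam, the investigator can ask the dosing study coordinator". That request is for disclosure of the allocation, after which open-label netarsudil is allowed in either arm. Table 1 gives the middle visit as "5 ± 1 weeks after DSO", and the visits on each side also have windows of one week either way. Section 2.1 sets the cap: "up to 60 FECD patients will be enrolled". Section 1.3 words the main outcome differently again, as a rate of clearing with no time point.

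**The concern.** With two primary time points, a trial can succeed on the first, on the second, on either, on both, or on a combination of the two. Each rule has its own error rate and power. The plan gives one error rate and one power but no rule, so a reader cannot tell which result would count as success. The rule could be settled after the data are seen.

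The visit schedule does not remove the doubt. Week 4 is the shared edge of the 3-week window (weeks 2 to 4) and the 5-week window (weeks 4 to 6). Week 6 is the shared edge of the 5-week window and the 7-week window (weeks 6 to 8). Three visits are therefore candidates, and the 5-week exam could stand for either named week.

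The choice of week also has consequences for what is compared. A week-6 value can fall after the 5-week exam, from which unmasking and open-label netarsudil are allowed. A week-4 value would mostly precede them.

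**Working it through.** **Inputs from section 3.2:** difference 0.8 − 0.6 = 0.20; SD 0.30; one-sided 5%; 29 per arm. **Assumed, not in the documents:** the same difference and SD at both weeks, a between-week correlation ρ of 0.5 to 0.9, and independent eyes.

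**1. The plan's own figure.** The standardised difference is 0.20/0.30 = 0.667. The normal approximation gives n = 2 × [(1.645 + 0.842)/0.667]² = 27.8 per arm. A two-sample t-test has power 79.3% at 28 per arm and 80.6% at 29, so 29 per arm is the t-test answer for one comparison. Enrolment: 58/(1 − 0.03) = 59.8, which rounds up to 60. The arithmetic is sound, and it covers a single test.

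**2. Two tests.** Treat the two test statistics as bivariate normal with correlation ρ. Write P(both) for the chance that both are significant. Each test alone has error 0.05 and power 0.806. For the power figures, the normal margins are set to match the t-test power. Then P(either) = 2 × P(one) − P(both).

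At ρ = 0.5:
- Under no effect, P(both) = 0.012, so the error for either week is 2 × 0.05 − 0.012 = 0.088.
- Under the assumed effect, P(both) = 0.695, so the power for either week is 2 × 0.806 − 0.695 = 0.917.

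**3. A split of the error rate.** At one-sided 2.5%, the power at each week with 29 per arm is 70.4%.

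**4. One test on the average of the two weeks.** The SD becomes 0.30 × √((1 + ρ)/2), which is 0.260, 0.277 and 0.292 at ρ = 0.5, 0.7 and 0.9.

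| Rule, 29 per arm | ρ = 0.5 | ρ = 0.7 | ρ = 0.9 |
|---|---|---|---|
| Either week at 5%: error | 8.8% | 8.0% | 6.8% |
| Either week at 5%: power | 91.7% | 89.1% | 85.5% |
| Both weeks at 5%: error if no effect at either week | 1.2% | 2.0% | 3.2% |
| Both weeks at 5%: power | 69.5% | 72.0% | 75.7% |
| Both weeks: n per arm for 80% power | 37 | 35 | 33 |
| 2.5% at each week: power for at least one | 84.6% | 81.3% | 76.6% |
| Average of the two weeks at 5%: power | 89.4% | 85.9% | 82.3% |

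Simulated t-tests (25,000 trials per case) at ρ = 0.5 and 0.9 agree: error for either week 9.1% and 7.0%; power for both weeks 68.7% and 75.5%. Using the plain normal approximation instead of the t-test, power for both weeks is 70.7% and 76.7%, with 36 and 32 per arm needed. The conclusion does not change.

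**5. Against the cap.** Requiring both weeks with 80% power needs 2 × 37 = 74 down to 2 × 33 = 66 evaluable patients. With the plan's 3% dropout that is 74/0.97 = 76.3 (77 enrolled) down to 66/0.97 = 68.04 (69 enrolled), against a cap of 60.

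**The case against.** The strongest reply is that week 4 was meant all along. The paragraph has one effect, one SD, one error rate and one sample size, and its enrolment sentence refers to the 4-week endpoint in the singular. On that reading the test has 5% error and 80.6% power. A fixed order starting at week 4, or one test on the average, also keeps both figures. A 2.5% split reaches 80% for at least one week when the correlation is no higher than roughly 0.7 to 0.8. Only unadjusted testing of either week, or a requirement for both, breaks a stated figure, and the plan states neither rule.

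This stands as far as it goes. No inflated error or lost power has been shown; what is shown is that the plan does not exclude them. But a phrase in a dropout sentence cannot override the formal definition at the start of the same paragraph, and the two conflict. Even with week 4 accepted, the plan does not say which visit supplies the value.

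It is also fair that the size rests on assumed inputs. Measurements two weeks apart may well be highly correlated, which points to the milder end (error near 6.8%, power near 76%). An equal difference at both weeks is doubtful for a proportion capped at 1 that rises with healing. Nor does week 6 always follow the 5-week exam, since that exam may itself take place at week 6.

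**Conclusion.** The concern holds. The endpoint definition contradicts the later wording in its own paragraph, matches no scheduled visit and carries no decision rule. The sample size supports one comparison only.

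If either week counts, the one-sided error is 8.8% to 6.8% instead of 5%. If both are required, power is 70% to 76% instead of 80%. Both ranges are for a correlation of 0.5 to 0.9 with equal effects at the two weeks. Rescue before the later assessment could shrink the later difference and lower the power for both weeks further. With week 4 alone, a fixed order or a single combined test, the stated figures survive. The plan should be corrected, but the defect is an unresolved choice and not an error in the sample-size calculation.

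**What to change.** Name one primary time point tied to a scheduled visit and make the others secondary. The 5-week exam, assessed before any unmasking, is a candidate. If it is chosen:

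1. Score eyes documented as fully cleared at the 3-week exam as fully cleared at week 5, because they may skip the 5-week exam.
2. Confirm that 0.6 versus 0.8 with SD 0.30 is the assumption for that visit, since section 3.2 ties it to no week.

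If week 4 is kept instead, state which visit supplies the value.

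If two time points are kept, test them in a fixed order: the earlier first, and the later only if the first is significant, each at one-sided 5%. State that the 80% power applies to the first test only. State also whether later values are used as observed regardless of open-label netarsudil.

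In either case, align the main outcome line in section 1.3 and the 4-week wording in section 3.2 with the choice.

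The cost is a short rewrite of the endpoint text, one scoring rule for skipped exams and one line in section 1.3. One time point loses its primary status. No extra visits or data are needed. No extra patients are needed if the assumed means and SD hold at the chosen visit; if they do not, the sample size has to be recalculated.

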**[contact], [contact]**

## **1. Purpose of the Study and Background**

### **1.1 Purpose of the Study:**

The study objective is to determine whether use of Rhopressa accelerates migration of host peripheral corneal endothelial cells to restore the central endothelial cell layer after removal of dysfunctional host endothelium and guttae-covered Descemet membrane from a central 4 to 5-mm diameter area to treat Fuchs endothelial corneal dystrophy (FECD).

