### **1.2 Background**

The leading reason for corneal transplantation in the United States is FECD, which is characterized by deposition of abnormal, vision-distorting deposits on Descemet membrane and subsequent apoptosis of corneal endothelial cells resulting in corneal edema. Deposition of guttae begins centrally and progresses peripherally. The current treatment for FECD is endothelial keratoplasty, in which a central 8-mm diameter area of Descemet membrane and dysfunctional endothelium is removed and replaced with healthy donor tissue. This results in rapid visual rehabilitation but requires long-term use of topical corticosteroids to prevent rejection of the donor endothelium. While the chance of rejection of the graft is reduced with Descemet's membrane endothelial keratoplasty (DMEK) relative to other corneal transplants, the risk is still present as is the risk of graft failure, requiring a repeat graft. If a patient's own cells could be used instead of donor tissue, then the need for long-term topical corticosteroids with the secondary risk of steroid-induced glaucoma would be reduced or eliminated.

The peripheral endothelium and Descemet membrane are often relatively healthy in FECD and studies have shown that the peripheral corneal endothelial cells can migrate to cover denuded areas. Therefore, some surgeons have investigated the possibility of removing the central dysfunctional endothelium and most densely guttae-covered area of Descemet membrane in FECD patients without implanting any donor tissue. When a 6-mm diameter area is stripped, the recovery tends to be slow and unreliable. Stripping a smaller area (4-mm diameter) accelerates recovery in many cases, yet some corneas still fail to fully clear within a reasonable time period and delayed clearing can lead to scar formation that degrades vision. A pilot study found that use of ROCK inhibitor eye drops (ripasudil, available outside the USA) resulted in faster and more reliable corneal clearing following Descemet stripping only (DSO) for FECD.

Unpublished data from outside the US indicates that Rhopressa™ may be superior to ripasudil for promoting endothelial cell migration and possible regeneration.

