Anticipated adverse events in subjects who had cataract surgery combined with DSO include cystoid macular edema and capsular haze. Cataract formation or progression is an anticipated adverse event in any eye that was phakic and underwent DSO without combined cataract surgery. These anticipated surgical adverse events will be recorded on the electronic case report form (eCRF) for each exam rather than on separate adverse event forms.

The most common anticipated adverse events associated with use of Rhopressa™ include: eye discomfort, irritation, itching or pain, foreign body sensation, increased tearing, blurry vision, conjunctival hyperemia, conjunctival hemorrhage, eyelid swelling, and verticillata. Additional adverse events reported with use of Rhopressa™ include: reduced visual acuity, allergic conjunctivitis, dry eye, keratitis, conjunctival swelling, photophobia, and corneal staining.

Adverse events: The type, severity, duration and frequency of the following anticipated adverse experiences and any other unanticipated ocular adverse events will be tabulated. If a patient experiences an adverse reaction, appropriate medical treatment will be provided. Examples may include:

- Intraocular pressure elevation which requires intervention
- Development of capsular haze which requires intervention
- Cystoid macular edema
- Iritis

Anticipated rare adverse events include retinal detachment, iris synechiae/atrophy, epiretinal membrane, infectious keratitis or conjunctivitis, branch retinal vein occlusion, or endophthalmitis.

Serious Adverse Event: A serious adverse event is one that results in any of the following outcomes: death, a life-threatening adverse event, inpatient hospitalization or prolongation of existing hospitalization, a persistent or significant disability/ incapacity, or a congenital anomaly/birth defect. In the event of a serious adverse event, the investigator will maintain complete documentation and promptly inform the study drug manufacturer and the governing Institutional Review Board (IRB) of the serious adverse event within their required reporting period.

Fellow eye: Patients in this population tend to be affected with the eye condition bilaterally, so many of the study subjects may undergo surgery on the fellow eye during study participation. Routine fellow-eye post-surgical complications will not be transcribed to the eCRF unless the fellow eye is enrolled in the study at the time of the event.

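### Section 3.2 names no primary model or covariate, and its sample size implies an unadjusted comparison, although pachymetry is already scheduled at screening

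*Combined protocol and SAP*

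**What the plan says.** Section 3.2 is the whole statistical plan. It defines the endpoint as the proportion of corneal clearing, gives a sample size, states the analysis population and names the software. The population sentence reads "Statistical analysis will be conducted on an intent-to-treat basis (i.e. all randomized subjects will be included in the analysis". No test, model or covariate is named, and nothing says whether the comparison is adjusted.

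The sample size is for a difference in means: the placebo "arm will be 0.6 vs. 0.8 in the Rhopressa arm", with a standard deviation of 0.30. "A sample size of 29 per study arm (total = 58) would provide 80% power" for a "difference between groups at a 5% significance level (one-sided test").

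Section 3.1 describes a computer-generated randomization table with assignment after consent. It mentions no stratification factor, and it assigns a participant's second eye to the opposite arm.

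Three sources of variation between eyes appear elsewhere:

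- Table 1 marks "Ultrasonic pachymetry" at screening. Section 3.1 allows routine screening measurements to be up to 90 days old at enrollment.
- Section 1.1 describes tissue removal "from a central 4 to 5-mm diameter area". Section 1.2 reports poor recovery after 6-mm stripping and says "Stripping a smaller area (4-mm diameter) accelerates recovery in many cases".
- Section 4.1 refers to "Anticipated adverse events in subjects who had cataract surgery combined with DSO", so some eyes may have both procedures and others not.

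**The concern.** With about 29 eyes per arm, differences between eyes at baseline go into the error term of a raw comparison of means. A chance imbalance in anything that predicts clearing also moves the estimate directly. The design does not protect balance through stratification, and the plan names no model that would correct for imbalance afterwards.

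Planned power is only just above 80%, on a one-sided test, so there is little slack. Leaving the model open has a further cost: covariates chosen after unmasking can be suspected of having been chosen for their effect on the result. That suspicion is avoided only if the model is written down beforehand.

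**Working it through.** **1. The plan's own figure.** Inputs from section 3.2: difference 0.80 − 0.60 = 0.20, SD 0.30, one-sided 5%, 29 per arm.

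- Standard error = 0.30 × √(2/29) = 0.079.
- Noncentrality = 0.20 / 0.0788 = 2.54, on 56 degrees of freedom.
- Noncentral-t power is 80.6% at 29 per arm and 79.3% at 28, so 29 is the smallest size that reaches 80%. The normal approximation gives 28 per arm.
- Dropout: 58 / 0.97 = 59.8, hence 60.

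The stated size is correct for an unadjusted two-sample t-test with independent eyes.

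**2. Adjusting for one baseline covariate.** Residual SD = 0.30 × √(1 − r²), where r is the within-arm correlation between screening pachymetry and proportion cleared. The documents give no r, so a range including zero is assumed. Degrees of freedom = 58 − 2 − 1 = 55.

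| r | Residual SD | Noncentrality | Power at 29 per arm |
|---|---|---|---|
| 0 | 0.300 | 2.54 | 80.6% (loss under 0.1 point) |
| 0.2 | 0.294 | 2.59 | 82.0% |
| 0.3 | 0.286 | 2.66 | 83.7% |
| 0.4 | 0.275 | 2.77 | 86.2% |
| 0.5 | 0.260 | 2.93 | 89.4% |

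**3. Chance imbalance.** The difference between arms in a standardized covariate has SD √(2/29) = 0.263.

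- It exceeds 0.25 SD in either direction in about 34% of randomizations, and 0.5 SD in about 6%.
- The shift in the unadjusted difference is r × 0.30 × imbalance. At 0.5 SD this is 0.2 × 0.30 × 0.5 = 0.03 for r = 0.2, and 0.5 × 0.30 × 0.5 = 0.075 for r = 0.5, against a planned difference of 0.20.

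**4. Stripped diameter.** The area ratio of 5 mm to 4 mm is (5/4)² = 1.56. Assume cells advance inward from the edge by x mm, so that the proportion cleared is 1 − (1 − 2x/D)².

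| x (mm) | D = 4 mm | D = 5 mm | Difference |
|---|---|---|---|
| 0.50 | 0.44 | 0.36 | 0.08 |
| 0.75 | 0.61 | 0.51 | 0.10 |
| 1.00 | 0.75 | 0.64 | 0.11 |
| 1.25 | 0.86 | 0.75 | 0.11 |

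- If half the eyes were at each extreme, the largest possible spread, the variance explained is (difference/2)² / 0.09. This runs from (0.0775/2)² / 0.09 = 1.7% to (0.11/2)² / 0.09 = 3.4%.
- Power then becomes about 81.2% to 81.7%, a gain of about one point at most.
- A 20-point imbalance in the share of 5-mm eyes moves the estimate by 0.20 × 0.11 = 0.02, about a quarter of the standard error.

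**The case against.** The strongest reply is that section 3.2 does not prescribe an unadjusted analysis. Its intent-to-treat sentence concerns only who is analysed, and sizing a trial on an unadjusted comparison is routine and does not rule out an adjusted one. That stands: the supportable statement is that no model is specified and that the sizing implies an unadjusted comparison. It does not remove the point, because an unspecified model also gives no pre-planned adjustment.

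Second, no passage says that screening thickness predicts clearing of a surgically stripped zone, and the value may be up to 90 days old at enrollment. This stands too. The gain could be near zero, but so is the cost.

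Third, a reader might infer that stripped diameter is a strong predictor and safe to adjust for because the trial is masked. The documents do not support either part:

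- The evidence in section 1.2 contrasts 4 mm with 6 mm, not differences within 4 to 5 mm. A 0.08 to 0.11 gap between individual eyes at the two extremes should not be set against a 0.20 difference between arm means.
- Actual diameter is set at surgery, after randomization, and is not listed as a study item in section 3.1 or Table 1.
- Section 3.1 masks the investigator but does not mention the surgeon as such. It also allows the first eye's assignment to be revealed at the 5-week exam. Because a second eye takes the opposite arm, its allocation could then be known before its surgery.

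Finally, section 4.1 links combined cataract surgery to macular edema and capsular haze, not to clearing, so it has no documented claim to a place in the primary model.

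**Conclusion.** The point holds as a missed, nearly costless improvement. The plan leaves the primary model open, does not stratify, and does not use a baseline measurement that it already schedules. On the plan's inputs, adjusting for pachymetry takes power from 80.6% to between 82.0% and 89.4% for assumed correlations of 0.2 to 0.5, with a loss under 0.1 point at zero. These figures assume independent eyes, a linear relation and a within-arm SD of 0.30; the correlation itself cannot be taken from the documents.

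A reader might go further and infer that the trial's result would be biased or its sample size wrong. Neither follows. The 29 per arm reproduces, and an unadjusted comparison of randomized groups is valid. The loss is of precision and of protection against chance imbalance.

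**What to change.** State in section 3.2 that the primary analysis is a linear model of the proportion cleared on treatment arm and that eye's screening central pachymetry, with a subject random effect (or equivalent) for participants who enrol both eyes. Name the time point or points to which the model applies, and give a rule for eyes without a screening value so that all randomized subjects stay in the analysis. Keep the unadjusted difference as a sensitivity analysis.

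If stripped diameter is wanted in the primary model, record the intended diameter before randomization and use that value. Otherwise keep actual diameter and combined cataract surgery for sensitivity analyses, and add both to the recorded items.

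The cost is a few sentences in section 3.2 and one degree of freedom for pachymetry, with no new examination. Recording diameter and combined surgery adds one or two fields to the case report form. The change should be dated before any unmasked comparison of the arms.
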